7.2. Participant Discontinuation/Withdrawal from the Study

A participant may withdraw from the study

- at any time at his/her own request
- at the request of his/her designee (eg, parents or legal guardian)
- at the discretion of the investigator for safety, behavioral, compliance, or administrative reasons
- if the participant becomes pregnant during the study
- if enrolled in any other clinical study involving an investigational product or enrolled in any other type of medical research judged not to be scientifically or medically compatible with this study
- if the participant, for any reason, requires treatment with another therapeutic agent that has been demonstrated to be effective for treatment of the study indication, discontinuation from the study occurs prior to introduction of the new agent, or
- receives a positive SARS-CoV-2 virus test or evidence of COVID-19 during the study

Discontinuation is expected to be uncommon.

At the time of discontinuing from the study, if possible, an early discontinuation visit should be conducted, as shown in the SoA. See the SoA (Section [1.3](#)) for data to be collected at the time of study discontinuation and follow-up and for any further evaluations that need to be completed. The participant will be permanently discontinued both from the study intervention and from the study at that time.

If the participant withdraws consent for disclosure of future information, the sponsor may retain and continue to use any data collected before such a withdrawal of consent. If a participant withdraws from the study, he/she may request destruction of any samples taken and not tested, and the investigator must document this in the site study records.

7.2.1. Discontinuation of Inadvertently Enrolled Participants

If the sponsor or investigator identify a participant who did not meet enrollment criteria and was inadvertently enrolled, then the participant should be discontinued from study treatment unless there are extenuating circumstances that make it medically necessary for the participant to continue on study treatment. If the investigator and the sponsor CRP agree it is medically

appropriate to continue, the investigator must obtain documented approval from the sponsor CRP to allow the inadvertently enrolled participant to continue in the study with or without treatment with investigational product. Safety follow-up is as outlined in Section 1.3 (Schedule of Activities), Section 8.2 (Safety Assessments), and Section 8.3 (Adverse Events and Serious Adverse Events) of the protocol.

7.3. Lost to Follow-up

A participant will be considered lost to follow-up if he or she repeatedly fails to return for scheduled visits and is unable to be contacted by the study site. Site personnel are expected to make diligent attempts to contact participants who fail to return for a scheduled visit or were otherwise unable to be followed up by the site.

Site personnel, or an independent third party, will attempt to collect the vital status of the participant within legal and ethical boundaries for all participants randomized, including those who did not get investigational product. Public sources may be searched for vital status information. If vital status is determined to be deceased, this will be documented, and the participant will not be considered lost to follow-up. Sponsor personnel will not be involved in any attempts to collect vital status information.

Discontinuation of specific sites or of the study as a whole are handled as part of Appendix 1 (see Section 10.1.7).

8. Study Assessments and Procedures

Study procedures and their timing are summarized in the SoA (Section 1.3.). Protocol waivers or exemptions are not allowed.

Immediate safety concerns should be discussed with the sponsor immediately upon occurrence or awareness to determine if the participant should continue or discontinue study intervention.

Adherence to the study design requirements, including those specified in the SoA, is essential and required for study conduct.

All screening evaluations must be completed and reviewed to confirm that potential participants meet all eligibility criteria. The investigator will maintain a screening log to record details of all participants screened and to confirm eligibility or record reasons for screening failure, as applicable.

Section 10.2 lists the laboratory tests that will be performed for this study.

Section 10.2.1 provides a summary of the maximum number and volume of invasive samples, for all sampling, during the study.

Unless otherwise stated in the subsections below, all samples collected for specified laboratory tests will be destroyed within 60 days of receipt of confirmed test results. Certain samples may be retained for a longer period, if necessary, to comply with applicable laws, regulations, or laboratory certification standards.

8.1. Efficacy Assessments

Not applicable.

8.2. Safety Assessments

Planned time points for all safety assessments are provided in the SoA (Section 1.3).

8.2.1. Physical Examinations

A complete or directed physical examination will be conducted according to the SoA (Section 1.3).

A complete physical examination will include, at a minimum, assessments of the cardiovascular, respiratory, GI, and neurological systems. Height and weight will also be measured and recorded at times noted in the SoA (Section 1.3).

A directed physical examination will include, at a minimum, assessments of the skin, lungs, cardiovascular system, and abdomen (liver and spleen).

Investigators should pay special attention to clinical signs related to previous serious illnesses.

8.2.2. Vital Signs

For each participant, vital signs measurements should be conducted according to the SoA (Section 1.3) and as clinically indicated.

It is suggested that systolic and diastolic blood pressure and heart rate should be measured in a supine position just after the ECG (if the ECG is recorded at the same time point) and for a

minimum of 10 minutes before any other procedures according to the SoA, (Section 1.3). These procedures should be performed prior to collection of blood samples if scheduled at the same time.

Unscheduled orthostatic vital signs should be assessed, if possible, during any AE of dizziness or posture-induced symptoms. Additional vital signs may be measured during each study period if warranted.

8.2.3. *Electrocardiograms*

For each participant, ECGs should be collected according to the SoA (Section 1.3).

Participants must be supine for approximately 10 minutes before ECG collection and remain supine but awake during ECG collection. Triplicate ECG's should be obtained approximately 1 minute between tracings. Electrocardiograms may be obtained at additional times, when deemed clinically necessary.

All ECGs recorded should be stored at the CRU.

Any clinically significant findings from ECGs that result in a diagnosis, and that occur after the participant receives the first dose of the investigational product, should be reported as an AE in the electronic data capture (EDC) system.

Electrocardiograms will be interpreted by a qualified physician (the investigator or qualified designee) at the CRU as soon after the time of ECG collection as possible, and ideally while the participant is still present, to determine whether the participant meets entry criteria at the relevant visit(s) and for immediate participant management, should any clinically relevant findings be identified.

If a clinically significant quantitative or qualitative change from baseline is identified after enrollment, the investigator will assess the participant for symptoms (eg, palpitations, near syncope, syncope) to determine whether the participant can continue in the study. The investigator or qualified designee is responsible for determining if any change in participant management is needed and must document his/her review of the ECG printed at the time of evaluation from at least 1 of the replicate ECGs from each time point.

8.2.4. *Clinical Safety Laboratory Assessments*

Refer to Section 10.2, Appendix 2 for the list of clinical laboratory tests to be performed and to the SoA (Section 1.3) for the timing and frequency.

The investigator must review the laboratory report, document this review, and record any clinically relevant changes occurring during the study in the AE section of the case report form (eCRF). The laboratory reports must be filed with the source documents. Clinically significant abnormal laboratory findings are those which are not associated with the underlying disease, unless judged by the investigator to be more severe than expected for the participant's condition.

All laboratory tests with values considered clinically significantly abnormal during participation in the study or within 72 hours after the last dose of study intervention should be repeated until the values return to normal or baseline or are no longer considered clinically significant by the investigator or medical monitor.

- If such values do not return to normal/baseline within a period of time judged reasonable by the investigator, the etiology should be identified and the sponsor notified.
- All protocol-required laboratory assessments, as defined in Appendix 2 (Section 10.2), must be conducted in accordance with the laboratory manual and the SoA.
- If laboratory values from non-protocol-specified laboratory assessments, performed at the institution's local laboratory require a change in participant management or are considered clinically significant by the investigator (eg, SAE or AE or dose modification), then the results must be recorded in the eCRF on the AEs page. Serious Adverse events will be reported on the Sponsor Form and faxed to Lilly Global Patient Safety.

8.2.5. Safety Monitoring

The sponsor will monitor safety data throughout the course of the study.

Lilly will review SAEs within the time frames mandated by company procedures. The medical monitor will periodically review the following data:

- trends in safety data
- laboratory analytes, and
- SAEs and non-SAEs, including monitoring of GI events, hypoglycemia, injection-site reactions, hypersensitivity reactions, and reported and adjudicated pancreatitis.

When appropriate, the Lilly medical monitor will consult with the functionally independent Global Patient Safety therapeutic area physician or clinical research scientist.

8.2.5.1. Hepatic Monitoring

Laboratory tests (Section 10.5, Appendix 5), including ALT, AST, ALP, TBL, direct bilirubin, GGT, and CK, should be repeated within 48 to 72 hours to confirm the abnormality and to determine if it is increasing or decreasing, if 1 or more of these conditions occur:

If a participant with baseline results of ...	develops the following elevations:
ALT or AST <1.5x ULN	ALT or AST \geq 3x ULN
ALP <1.5x ULN	ALP \geq 2x ULN
TBL <1.5x ULN	TBL \geq 2x ULN (except for participants with Gilbert's syndrome)
ALT or AST \geq 1.5x ULN	ALT or AST \geq 2x baseline
ALP \geq 1.5x ULN	ALP \geq 2x baseline
TBL \geq 1.5x ULN	TBL \geq 2x baseline (except for participants with Gilbert's syndrome)

Abbreviations: ALP = alkaline phosphatase; ALT = alanine aminotransferase; AST = aspartate aminotransferase; TBL = total bilirubin; ULN = upper limit of normal.

If the abnormality persists or worsens, clinical and laboratory monitoring, and evaluation for possible causes of abnormal liver tests, should be initiated by the investigator in consultation with the Lilly-designated medical monitor. At a minimum, this evaluation should include physical examination and a thorough medical history, including symptoms, recent illnesses (eg, heart failure, systemic infection, hypotension, or seizures), recent travel, history of concomitant medications (including over-the-counter), herbal and dietary supplements, and history of alcohol drinking and other substance abuse.

Initially, monitoring of symptoms and hepatic biochemical tests should be done at a frequency of 1 to 3 times weekly, based on the participant's clinical condition and hepatic biochemical tests. Subsequently, the frequency of monitoring may be lowered to once every 1 to 2 weeks if the participant's clinical condition and lab results stabilize. Monitoring of ALT, AST, ALP, and TBL should continue until levels normalize or return to approximate baseline levels.

8.3. Adverse Events and Serious Adverse Events

Adverse events will be reported by the participant (or, when appropriate, by a caregiver, surrogate, or the participant's legally authorized representative).

The investigator and any qualified designees are responsible for detecting, documenting, and recording events that meet the definition of an AE or SAE, and they remain responsible for following up AEs that are serious, considered related to the study intervention or study procedures, or that caused the participant to discontinue the study intervention or study (see Section 7).

8.3.1. Time Period and Frequency for Collecting AE and SAE Information

All SAEs will be actively collected from the signing of the ICF until the follow-up visit at the time points specified in the SoA (Section 1.3) and until 30 days after the last dose for spontaneously reported SAEs.

All AEs will be collected from the signing of the ICF until the follow-up visit OR participation in the study has ended.

Adverse events that begin before the start of study intervention but after signing of the ICF will be recorded on the AE CRF.

Although all AEs after signing the ICF are recorded by the site in the CRF/electronic data entry, SAE reporting to the sponsor begins after the participant has signed the ICF and has received study intervention. However, if an SAE occurs after signing the ICF, but prior to receiving study intervention, it needs to be reported ONLY if it is considered reasonably possibly related to study procedures.

All SAEs will be recorded and reported to the sponsor or designee immediately, and under no circumstance should this exceed 24 hours, as indicated in Appendix 3 (Section 10.3). The investigator will submit any updated SAE data to the sponsor within 24 hours of it being available.

Investigators are not obligated to actively seek AEs or SAEs after conclusion of the study participation. However, if the investigator learns of any SAE, including a death, at any time after a participant has been discharged from the study and he/she considers the event to be reasonably

related to the study intervention or study participation, the investigator must promptly notify the sponsor.

Pregnancy (maternal or paternal exposure to the study intervention) does not meet the definition of an AE. However, to fulfill regulatory requirements, any pregnancy should be reported following the SAE process to collect data on the outcome for both mother and fetus.

The designated medical monitor of the sponsor will monitor safety data throughout the course of the study. The sponsor and/or its designee will review SAEs within appropriate timeframes to meet reporting obligations imposed by regulatory authorities. All SAEs and unexpected AEs for this study will be reported to regulatory authorities in accordance with local laws, directives, and regulations (Section 8.3.4).

8.3.2. Method of Detecting AEs and SAEs

The method of recording, evaluating, assessing causality of AE and SAE, and the procedures for completing and transmitting SAE reports are provided in Appendix 3 (Section 10.3).

Care will be taken not to introduce bias when detecting AEs and/or SAEs. Open-ended and non-leading verbal questioning of the participant is the preferred method to inquire about AE occurrences.

8.3.3. Follow-up of AEs and SAEs

After the initial AE/SAE report, the investigator is required to proactively follow each participant at subsequent visits/contacts. All SAEs will be followed until resolution, stabilization, the event is otherwise explained, or the participant is lost to follow-up (as defined in Section 7.3). Further information on follow-up procedures is provided in Appendix 3 (Section 10.3).

8.3.4. Regulatory Reporting Requirements for SAEs

Prompt notification of an SAE by the investigator to the sponsor is essential so that legal obligations and ethical responsibilities towards the safety of participants and the safety of a study intervention under clinical investigation are met.

The sponsor has a legal responsibility to notify both the local regulatory authority and other regulatory agencies about the safety of a study intervention under clinical investigation. The sponsor will comply with country-specific regulatory requirements relating to safety reporting to the regulatory authority, Institutional Review Boards (IRBs)/Independent Ethics Committees (IECs), and investigators.

An investigator who receives an investigator safety report describing an SAE or other specific safety information (eg, summary or listing of SAEs) from the sponsor will review and then file it along with the IB and will notify the IRB/IEC, if appropriate according to local requirements.

8.3.5. Pregnancy

Details of all pregnancies in female participants will be collected after the start of study intervention and until 30 days after the final visit, which corresponds to more than 5 terminal half-lives after the last dose of LY3526318.

Details of all pregnancies in female partners of male participants will be collected until 90 days after last administration of LY3526318.

If a pregnancy is reported, the investigator should inform the sponsor within 24 hours of learning about the pregnancy and should follow the procedures outlined Appendix 4 (Section 10.4).

Abnormal pregnancy outcomes (eg, spontaneous abortion, fetal death, stillbirth, congenital anomalies, ectopic pregnancy) are considered SAEs.

8.3.6. Product Complaints

A product complaint is any written, electronic, or oral communication that alleges deficiencies related to the identity, quality, durability, reliability, safety, effectiveness, or performance of a trial intervention.

The sponsor collects product complaints on investigational products used in clinical studies in order to ensure the safety of study participants, monitor quality, and to facilitate process and product improvements.

Participants will be instructed to contact the investigator as soon as possible if he or she has a complaint or problem with the investigational product so that the situation can be assessed.

NOTE: AEs/SAEs that are associated with a product complaint will also follow the processes outlined in Section 8.3.3 and Appendix 10.3 of the protocol.

8.3.6.1. Time Period for Detecting Product Complaints

Product complaints that result in an AE will be detected, documented, and reported to the sponsor during all periods of the study in which the drug is used.

If the investigator learns of any product complaint at any time after a participant has been discharged from the study and such incident is considered reasonably related to a drug provided for the study, the investigator will promptly notify the sponsor.

8.3.6.2. Prompt Reporting of Product Complaints to Sponsor

Product complaints will be reported to the sponsor within 24 hours after the investigator becomes aware of the complaint.

The Product Complaint Form will be sent to the sponsor by the method provided in the form. If the primary method is unavailable, then an alternative method provided in the form should be utilized.

8.3.6.3. Follow-up of Product Complaints

Follow-up applies to all participants, including those who discontinue study intervention.

The investigator is responsible for ensuring that follow-up includes any supplemental investigations, as indicated, to elucidate the nature and/or causality of the product complaint.

New or updated information will be recorded on the originally completed form with all changes signed and dated by the investigator and submitted to the sponsor.

8.4. Treatment of Overdose

An overdose is not anticipated in the study, as a trained CRU member will administer all study intervention.

In case of overdose, use supportive therapy. There is no known antidote to LY3526318 therapy.

Any dose of LY3526318 greater than the daily dose assigned through randomization will be considered an overdose. Treatment for overdose is supportive care.

In the event of an overdose, the investigator should

1. contact the medical monitor immediately
2. closely monitor the participant for any AE/SAE and laboratory abnormalities until LY3526318 can no longer be detected systemically (at least 14 days)
3. obtain a plasma sample for PK analysis within 14 days from the date of the last dose of study intervention if requested by the medical monitor (determined on a case-by-case basis), and
4. document the quantity of the excess dose, as well as the duration of the overdose, in the CRF.

Decisions regarding dose interruptions or modifications will be made by the investigator in consultation with the medical monitor based on the clinical evaluation of the participant.

8.5. Pharmacokinetics

For all participants, blood samples of up to 3 mL each for the determination of concentrations in plasma of LY3526318 and metabolite(s) of interest will be collected at time points specified in the SoA (Section 1.3). Instructions for the collection and handling of blood samples will be provided by the sponsor.

Sampling times for PK evaluation are provided as a guidance to be adhered to as closely as possible. The actual date and time (24-hour clock time) of each sample collection must be recorded. Predose samples should be obtained between waking up and dosing. The sampling schedule may be modified following a review of PK data from the initial cohorts.

A maximum of 3 additional PK samples may be drawn at other time points during the study if warranted and agreed upon by both the investigator and the sponsor. A PK sample should be obtained at the early termination visit, if applicable.

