Abbreviations: C = complete physical examination; Con med = concomitant medications; COVID-19 = coronavirus disease 2019; CRU = clinical research unit; C-SSRS = Columbia-Suicide Severity Rating Scale; D = directed physical examination; ECG = electrocardiogram; ED = early discontinuation; FU = safety follow-up; HBsAg = hepatitis B surface antigen; β-hCG = beta subunit of human chorionic gonadotropin; HCV = hepatitis C virus; HIV = human immunodeficiency virus; P = predose assessment; PK = pharmacokinetic; S = Screening; SOP = standard operating procedure.

^a Participants who discontinue the study prior to study completion will be expected to complete the ED visit procedures.

- b Day -1 procedures can be performed on a day prior to dosing or predose on day of dosing.
- c Participants will be confined to the CRU from Day -1 until all study assessments are completed 72 hours after the last dose
- d After participants have completed the required in-house stay, the remaining activities may be completed in house or ambulatory based upon the discretion of the investigator.
- e A standard urine dipstick may be used.
- f A single 12-lead ECG will be obtained in the supine position after at least 10 minutes rest.
- g The exact time study intervention is administered will be recorded.
- h See [Table 4](#) Part B Scheduled Times for PK Blood Samples.

Note: Screening visits will be performed within 28 days before the administration of first dose.

Note: In the event that assessments are planned for the same time, assessments should be conducted in following order: ECG/vital signs/PK sample. The ECG and vital signs measurement can be obtained at least 30 minutes prior to the PK sample, which is drawn at the nominal time point.

Note: All local requirements regarding COVID-19 will be followed according to local/site SOP.

Table 4. Part B Scheduled Times for PK Blood Samples and Single 12-lead ECGs

Day	Time ^a	PK Collections ^b	ECG (fasted)	ECG (fed)
Day 1	Predose	X	X	X
	Dose	Dose of LY3526318		
	1 h	X		
	2 h	X	X	
	4 h	X	X	X
	6 h	X	X	X
	8 h	X		
	12 h	X		
Day 2	Predose (24 hours after the preceding dose)	X	X	X
	Dose	Dose of LY3526318		
Day 3	Predose (24 hours after the preceding dose)	X		
	Dose	Dose of LY3526318		
Day 4	Predose (24 hours after the preceding dose)	X		
	Dose	Dose of LY3526318		
Day 5	Predose (24 hours after the preceding dose)	X	X	X
	Dose	Dose of LY3526318		
	1 h	X		
	2 h	X	X	
	4 h	X	X	X
	6 h	X	X	X
	8 h	X		
	12 h	X		

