Day 6	+24 h (24 hours after the preceding dose)	X	X	X
Day 7	+ 48 h	X		
Day 8	+72 h	X		
Follow-Up		X		
Early Discontinuation		X	X	X

Abbreviations: ECG = electrocardiogram; PK = pharmacokinetic.

a Sampling times are given as targets to be achieved within reasonable limits.

b The timing of PK sample collections may be adjusted based on clinical needs. The exact sample collection dates and times must be recorded.

2. Introduction

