6.3.2. Selection and Timing of Doses

All doses of the study intervention will be administered at the CRU approximately between 0800 hours and 1100 hours.

A trained CRU personnel member will administer all doses of the study intervention at the CRU.

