16.1.1.2 Parameters

- Plasma PK parameters for LY3526318 as defined in [Table 2](#)
- Plasma PK parameters for LSN3528305 as defined in [Table 2](#)

Table 2: Plasma PK Parameters

Parameter	Description	SAD	MD Day 1	MD Day 5	SAS Programming Notes
C_{max}	Maximum plasma concentration. Observed peak analyte concentration obtained directly from the experimental data without interpolation, expressed in concentration units.	✓	✓	✓	Cmax from WNL
T_{max}	Time to maximum plasma concentration. First observed time to reach peak analyte concentration obtained directly from the experimental data without interpolation, expressed in hours(h).	✓	✓	✓	Tmax from WNL
AUC_{0-t}	Area under the concentration-time curve (time 0 to time of last quantifiable concentration).	✓			AUClast from WNL
AUC_{0-inf}	Area under the plasma concentration-time curve (time 0 to infinity). Percent extrapolation less than or equal to 20% is required to obtain a reliable AUC_{0-inf} .	✓			AUCINF_obs from WNL If $AUC_ \%Extrap_obs > 20\%$ then parameter is flagged
AUC_{0-24}	Area under the plasma concentration-time curve from time 0 to 24 hours post-dose.	✓			AUC_{0-24} from WNL where partial time =24h, if missing for a participant then AUC at nominal time 24h from summary file is used for AUC_{0-24}
AUC_{0-tau}	Area under the plasma concentration-time curve over the dosing interval (time 0 to 24h) at steady state.		✓	✓	AUC_{tau} from WNL where tau is equal to 24h, if missing for a participant then AUC at nominal time 24h from summary file is used for AUC_{0-tau}
λ_z	Terminal phase rate constant calculated by linear regression of the terminal log-linear portion of the concentration vs. time curve. Linear regression of at least 3 points and an adjusted r^2 greater than 0.80 are required to obtain a reliable λ_z .	✓		✓	Lambda_z from WNL If Rsq adjusted $\leq .80$ then parameter is flagged
$t_{1/2}$	Terminal phase half-life expressed in hour (h). Percent extrapolation less than or equal to 20% and adjusted r^2 greater than 0.80 is required to obtain a reliable $t_{1/2}$.	✓		✓	HL_Lambda_z from WNL If $AUC_ \%Extrap_obs > 20\%$ or Rsq adjusted ≤ 0.80 then parameter is flagged

Parameter	Description	SAD	MD Day 1	MD Day 5	SAS Programming Notes
CL/F	Apparent oral clearance, calculated as Dose/AUC _{0-inf} for SAD regimens or Dose/AUC _{0-tau} for the MAD regimen on Day 5; LY3526318 only	✓		✓	CL_F_obs or CLss_F from WNL respectively. If AUC_%Extrap_obs > 20% or Rsq adjusted ≤ 0.80 then parameter is flagged

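### Part B Day 1 AUC0-tau can be cut short, and the accumulation ratio inflated, when the Day 2 predose sample is early and the SAP's fallback for a missing AUC_tau applies

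*Protocol*

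**What the plan says.** **Sampling.** Protocol section 8.5 gives one rule for all predose samples: "Predose samples should be obtained between waking up and dosing". It gives no width in hours. The same paragraph also says "Sampling times for PK evaluation are provided as a guidance to be adhered to as closely as possible". In Protocol Table 4 (section 1.3), the Part B Day 2 to 5 predose rows are each tied to a time of 24 h after the last dose. The table's footnote adds "Sampling times are given as targets to be achieved within reasonable limits", again without a number. Section 6.3.2 places dosing "approximately between 0800 hours and 1100 hours".

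**Day 1 profile.** Table 4 samples at predose and at 1, 2, 4, 6, 8 and 12 h, then at the Day 2 predose time. Nothing else is scheduled between 12 h and the second dose.

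**Day 5 profile.** The 24 h sample on Day 6 is not a predose sample, and 48 h and 72 h samples follow.

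**Analysis.** SAP Table 2 (section 16.1.1.2) defines AUC0-tau for MD Day 1 and Day 5 as "AUC_{tau} from WNL where tau is equal to 24h, if missing for a participant then AUC at nominal time 24h". Lambda-z is ticked for SAD and MD Day 5 but not for MD Day 1. AR_AUC is Day 5 AUC0-tau divided by Day 1 AUC0-tau. SAP section 16.2.2 uses actual sampling times for parameter calculation. SAP section 16.2.1 summarises concentrations, and plots their geometric means, by scheduled time.

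**The concern.** The two protocol statements give the Day 2 to 5 predose samples different windows. Sites that follow section 8.5 could draw them well before 24 h. A predose sample must precede the next dose, so when doses are given at the same clock time each day the sample can fall only at or before 24 h. The timing error is then one-sided. If it comes from unit routine, all six active participants share it.

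The SAP fallback turns that timing error into a bias. It carries AUC to whenever the nominal 24 h sample was drawn and labels the result AUC0-tau. It sets no tolerance, extends nothing to 24 h and raises no flag. Only the Day 1 value is exposed, so the shortfall enters the denominator of AR_AUC and nothing in the numerator offsets it. AUC is a primary endpoint of Part B, and the same rule applies to the metabolite LSN3528305.

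The concentration tables have a related problem that does not depend on the fallback: an early sample is tabulated as a 24 h value.

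**Working it through.** The documents state no expected accumulation ratio or bias, so there is no planned figure to reproduce.

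**Inputs**
- Half-life 9.72 to 13.5 h (Protocol section 2.2, prior formulation). It is an assumption that the new formulation is similar.
- Sampling grid: Part B Day 1, Protocol Table 4.
- AUC rule: linear up/log down (note to SAP Table 2).
- e = hours by which the Day 2 predose sample precedes 24 h. The documents give no value, so a range is shown. A value of 3 h corresponds to a dose at 1100 followed by a sample at 0800 the next day.

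**Step 1: hand check, mono-exponential decline.** With k = ln 2 / half-life, the share of AUC0-24 lost is

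[exp(-k(24-e)) - exp(-24k)] / [1 - exp(-24k)].

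- Half-life 9.72 h: k = 0.0713 and exp(-24k) = 0.1806. For e = 2, (0.2083 - 0.1806)/0.8194 = 3.4%.
- Half-life 13.5 h: k = 0.0513 and exp(-24k) = 0.2916. For e = 2, (0.3232 - 0.2916)/0.7084 = 4.5%.

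**Step 2: allow for absorption.** A one-compartment oral model on the Table 4 grid, with linear PK and an assumed absorption rate of 0.25 to 1.5 per hour, gives the following when the fallback is used:

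| Actual time of sample | Day 1 AUC0-tau | AR_AUC |
|---|---|---|
| 23.5 h | -0.9 to -1.5% | +0.9 to +1.5% |
| 23 h | -1.8 to -2.9% | +1.8 to +3.0% |
| 22 h | -3.6 to -6.1% | +3.8 to +6.4% |
| 21 h | -5.7 to -9.3% | +6.0 to +10.3% |

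With a full 24 h on Day 1, the modelled ratio is 1.24 to 1.34 (half-life 9.72 h) or 1.43 to 1.58 (half-life 13.5 h).

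**Step 3: is Day 5 exposed?** No. If its 24 h sample is early, the 48 h and 72 h samples allow AUC to be read at exactly 24 h, and lambda-z is derived.

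**Step 4: when can a Day 1 slope be fitted?** SAP section 16.2.2 requires at least three points, excluding Cmax. A Tmax of 6 h or earlier leaves 8 h, 12 h and the Day 2 predose sample. A Tmax of 8 h or later leaves fewer than three.

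**Step 5: would a slope extension work?** For a sample at 21 h, extending to 24 h with the slope of the last three points leaves an error of at most about 0.5%. That worst case is the slowest absorption, where the peak falls at 8 h and one of the three points is Cmax, so the SAP's three-point rule would not be met. For absorption rates of 0.5 per hour or more the error is below 0.1%.

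**Step 6: tabulated concentrations.** The excess over the true 24 h value is 2^(e/half-life) - 1. For e = 2 this is 2^(2/9.72) - 1 = 15% and 2^(2/13.5) - 1 = 11%.

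**The case against.** **Timing is not left open.** A reader might infer that these samples may be drawn at any time in the morning. The documents do not support that. Section 8.5 itself asks for close adherence, Table 4 gives 24 h as the target, and a note to the Part B schedule says that when assessments coincide the PK sample is the one taken at its nominal time. An ECG is scheduled at Day 2 predose, so that note covers this sample. This point stands. What remains is a conflict of wording and a tolerance with no number.

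**The fallback is conditional.** A reader might infer that every early sample lowers Day 1 AUC0-tau. It does not, because the first choice is AUC "from WNL where tau is equal to 24h". Nor does the missing lambda-z tick for MD Day 1 show that AUC_tau will usually be missing. It shows that the parameter is not reported for that day, not that no slope may be fitted. This also stands. The SAP does not say when AUC_tau counts as missing, so the frequency cannot be judged either way.

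**Dosing may be later than 24 h after the previous dose.** In that case the predose sample need not be early.

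**Two extensions do not hold.** A reader might extend the point to SAD AUC0-24, which has similar fallback wording. There, sampling continues to 48, 72 and 96 h, so the 24 h sample is not the last point. A reader might also infer harm to a steady-state assessment from troughs. SAP Table 2 has no trough parameter and no such analysis is planned.

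**Little hangs on it.** AR_AUC is not a protocol endpoint, the analysis is descriptive, Part B has six active participants and between-participant variability is high. Actual times are recorded and sampling-time deviations are listed. This is fair and limits the weight of the point. But a listing makes an early sample visible without correcting the AUC, and a one-sided error shared across participants does not average out.

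**Conclusion.** The point holds conditionally. Section 8.5 permits timing that Table 4 does not intend, and the SAP fallback accepts that timing without a limit. When the Day 2 predose sample is early **and** AUC_tau is missing, Day 1 AUC0-tau is understated and AR_AUC overstated. If either condition is absent, this bias does not arise.

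The Day 1 shortfall is about 1-3% for a sample 0.5 to 1 h early, about 3-6% at 2 h and about 6-9% at 3 h, with a slightly larger relative rise in AR_AUC. These figures rest on linear one-compartment kinetics, the prior formulation's half-lives and the assumed absorption rates. The documents give no half-life or Tmax for the metabolite, so its figures are unknown.

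The effect on tabulated concentrations needs only the early sample: about 11-15% at 2 h.

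The likely effect is modest. It is still worth correcting, because the error has a known direction, affects a primary Part B endpoint and costs almost nothing to remove.

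**What to change.** 1. **Protocol section 8.5 (or the site manual).** Limit the waking-to-dosing window to predose samples before a first dose. Require the Part B Day 2 to 5 predose samples shortly before that day's dose, at the 24 h nominal time in Table 4.
2. **SAP Table 2, MD Day 1 AUC0-tau.** Replace the fallback. When the last sample is before 24.0 h, extend AUC log-linearly to exactly 24 h with the post-peak slope, deriving lambda-z on Day 1 for this purpose. If no slope can be estimated, flag the value and the AR_AUC based on it.

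No change is needed for SAD AUC0-24 on this ground.

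The cost is one sentence in the protocol or site manual and one SAP programming note, with no extra samples or visits.
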